### 3.3.3. ADCS-CGIC

The ADCS-CGIC ([Schneider et al. 1997](#)) is a single-question clinician-completed scale for assessing clinically relevant global change in patients with dementia based on an organized but unstructured assessment of the participants's function and mental status, a caregiver interview, and a standardized set of questions. The ADCS CGIC evaluation will be performed by an Investigator who is blinded to other cognitive evaluations. The ADCS-CGIC score takes values from 1 to 7, with higher scores representing greater worsening, centered on a score of 4 for no change from baseline.

### 3.3.4. ADAS-cog

The ADAS-cog is the 11-item cognitive subscale of the Alzheimer's Disease Assessment Scale (ADAS; [Rosen et al. Am J Psychiatry 1984](#)) designed to measure the severity of the most prominent symptoms of dementia in patients with Alzheimer's disease (AD). The ADAS-cog subscale measures alterations of memory, language, praxis, attention and other cognitive abilities which comprise the core symptoms of AD and PDD through a series of clinician-administered tests. This study utilizes an early revision of the ADAS-cog (unpublished manual [Mohs, 1994](#); see: <http://adni.loni.usc.edu/data-samples/data-faq/>) and does not include the supplemental delayed word recall or number cancellation tasks (cf. [Petersen et al. 2005](#)) nor the maze task (cf. [Mohs et al. 1997](#)). Item-level scores from the 11 tasks are summed for a total score (range 0 to 70) with higher scores representing worse cognitive function.

### 3.3.5. PDAQ-15

The PDAQ-15 ([Brennan et al. 2016](#)) is a 15-item scale completed by a knowledgeable informant and designed to measure cognitive instrumental activities of daily living. Each item is rated from 0 (Cannot Do) to 4 (None [=no difficulty doing]). All items are summed for a total score (range 0 to 60) with higher scores indicating greater ability to perform instrumental activities of daily living.

### 3.3.6. SAPS-PD

The SAPS-PD ([Voss et al. 2013](#)) is a 9-item clinician-rated scale consisting of a subset of items (H1 Auditory Hallucinations, H3 Voices Conversing, H4 Somatic or Tactile Hallucinations, H6 Visual Hallucinations, H7 Global Rating of Severity of Hallucinations, D1 Persecutory Delusions, D2 Delusions of Jealousy, D7 Ideas and Delusions of Reference, D13 Global Rating of Severity of Delusions) selected on the basis of their relevance to PDD from the full 20-item SAPS ([Andreasen, 1984](#)) and designed to measure positive symptoms in patients with schizophrenia. Each item is rated from 0 (absent) to 5 (severe). All items are summed for a total score (range 0 to 45) with higher scores indicating more severe positive symptoms.

### 3.3.7. SCOPA-SLEEP

The SCOPA-SLEEP ([Marinus et al. 2003](#)) is a 13-item self-reported scale designed to evaluate nighttime sleep and daytime sleepiness among patients with PD. The SCOPA-SLEEP consists of four sections: (a) a single question (range 0 to 3) addressing the frequency of using sleeping tablets; (b) 5 questions addressing specific elements of nighttime sleep quality; (c) one question evaluating overall nighttime sleep quality over the previous month, and (d) 6 questions addressing daytime sleepiness. The 5 nighttime sleep questions rate the perceived extent of problems with sleep fragmentation, sleep efficiency, sleep duration, and early wakening, each rated from 0 (not at all) to 3 (a lot). They are summed for a total score (range 0 to 15) with higher scores indicating greater problems with nighttime sleep. The overall sleep quality question is rated on a 7-point scale (range 0 to 6) with higher scores indicating worse sleep quality. The 6 daytime sleepiness questions rate the frequency of experiences indicative of sleepiness, each rates from 0 (never) to 3 (often). They are summed for a total score (range 0 to 18) with higher scores indicating greater daytime sleepiness.

### 3.3.8. NPI

The NPI ([Cummings et al. 1994](#), [Cummings 1997](#), [Kaufer et al. 1998](#)) is a caregiver-completed scale designed to evaluate 12 subdomains of behavioral functioning: delusions, hallucinations, agitation, dysphoria, anxiety, apathy, irritability, euphoria, disinhibition, aberrant motor behavior, night-time behavior disturbances, and appetite and eating abnormalities. Each domain has a screening question that assesses the presence of the specific disturbance. If present, a series of 7 to 9 more detailed Yes/No subquestions are asked, the frequency is rated on a scale from 1 (occasionally, less than once per week) to 4 (very frequently, once or more per day or continuously), the severity is rated on a scale from 1 (mild) to 3 (marked), and caregiver emotional distress is rated on a scale from 0 (not at all [distressed]) to 5 (very severely or extremely [distressed]). The total score for each domain (range 0 to 12) is calculated by multiplying the frequency by the severity or given a value of zero if presence of the disturbance for that domain was not endorsed. A total NPI score is calculated by adding all domain-specific total scores together (range 0 to 144) with higher scores indicating worse neuropsychiatric disturbance. A total caregiver distress score (NPI-D, range 0 to 60) is calculated by adding all domain-specific caregiver distress scores.

### 3.3.9. MoCA

The MoCA ([Nasreddine et al. 2005](#)) consists of 8 clinician-administered cognitive tasks designed to screen for mild cognitive impairment. The MoCA assesses attention and concentration, executive functions, memory, language, visuoconstructional skills, conceptual thinking, calculations, and orientation. One point is awarded for correct completion of each item of the visuospatial/executive function task (5 items), naming task (3 items), digit vigilance and tapping items of the attention task (3 items), the sentence repetition items of the language task (2 items), abstraction task (2 items), delayed recall task (5 items), and orientation task (6 items). One point is awarded for naming 11 or more words during the fluency item of the language task. Zero (none correct) to 3 (4 or more correct) points are awarded based on the number of correct subtractions by 7 starting at 100 in the attention task. One point is awarded if the participant has 12 years or less of education unless the score is already 30. Scores for each task are summed for a total score (range 0 to 30) with higher scores indicating greater cognitive capacity.

### 3.3.10. UPDRS

The UPDRS ([Fahn et al. 1987](#)) is a 4-part, clinician-completed scale: Part I, Mentation, Behavior and Mood; Part II, Activities of Daily Living; Part III, Motor Examination; Part IV, Complications of Therapy. Each item in Parts I (4 items), II (13 items), and III (27 items) is rated on a scale from 0 (normal, none, or condition absent; text varies by item) to 4 (the most severe state of a given condition; text varies by item). The items are summed separately by Part and across all three parts for four total scores (range Part I, 0 to 16; Part II, 0 to 52; Part III, 0 to 108; Parts I-III, 0 to 176) with higher scores indicating more severe impairments. Part IV contains 11 items divided across three subsections: A, Dyskinesias (4 items); B, Clinical Fluctuations (4 items); and C, Other Complications (3 items). Part IV A consists of 3 items rated on a scale from 0 (no experience of a given condition; text varies by item) to 4 (the most severe state of a given condition; text varies by item) and 1 item rated on a scale from 0 (no; condition not present) to 1 (yes; condition present). Part IV B consists of 1 item rated on a scale from 0 (none) to 4 (76 to 100% of the day) and 3 items rated on a scale from 0 (no; condition not present) to 1 (yes; condition present). Part IV C consists of 3 items rated on a scale from 0 (no; condition not present) to 1 (yes; condition present). The items are summed separately by subsection and across all Part IV items for four total scores (range Part IV A, 0 to 13; Part IV B, 0 to 7; Part IV C, 0 to 3; Part IV, 0 to 23) with higher scores indicating more severe complications.

### 3.3.11. Orthostasis

Orthostatic hypotension will be defined as a maximum decrease of 20 mm Hg or greater in systolic blood pressure (SBP) or a maximum decrease of 10 mm Hg or greater in diastolic blood pressure (DBP) when moving from a supine to a standing position, with measurements completed 1 min and 3 min after standing.

### 3.3.12. Levodopa Equivalent Daily Dosage

The levodopa equivalent daily dosage (LEDD) will be calculated using data from the concomitant medications log. The conversion from dopaergic drugs other than carbidopa-levodopa will follow the recommendations by [Tomlinson et al. \(2010\)](#) with the following additions for more recently approved drugs.

- Extended release formations of carbidopa-levodopa (Rytary™) will be converted at 60% of their actual levodopa content (which is 5 mg greater than their labeled content) based on mean post-baseline daily dosages reported in [Hauser et al. \(2013\)](#);
- Extended release formations of ropinirole (RequipXL™) will be converted at 20 mg levodopa equivalent per mg ropinirole based on equivalent maximum recommended daily dosage.

The full calculation is as follows:

1. At each time any oral levodopa is taken per day, calculate the immediate release levodopa (e.g., Sinemet, Parcopa) dosage (mg) based on the number of tablets taken per dose and the dosage of levodopa in each tablet
2. At each time any oral levodopa is taken per day, calculate the controlled release levodopa (e.g., Sinemet CR) dosage (mg) and multiply by 0.75 to account for loss of bioavailability

3. At each time any oral levodopa is taken per day, calculate the extended release levodopa (e.g., Rytary) dosage (mg), noting that the listed dosage per tablet is 5 mg less than the actual dosage, and multiply by 0.60 to account for loss of bioavailability
4. At each time any oral levodopa is taken per day, calculate the total daily oral levodopa dosage by summing together the oral levodopa dosage from immediate release, controlled release, and extended release formulations (quantities 1 through 3)
5. At each time any oral levodopa is taken per day, if entacapone but not tolcapone is taken at the same time, either separately or as a combination drug (e.g., Stalevo), then multiply the total levodopa dosage at that time (quantity 4) by 0.33
6. At each time any oral levodopa is taken per day, if tolcapone (e.g., Tasmar) is taken at the same time, then multiply the total levodopa dosage at that time (quantity 4) by 0.50
7. Calculate the COMT-adjusted total daily levodopa equivalent dosage associated with oral levodopa as the sum over all time points of quantities 4 through 6
8. If enteral levodopa is taken without any COMT inhibitor, then multiply the total enteral levodopa (e.g., Duopa) daily dosage (mg) by 1.11
9. If enteral levodopa is taken with entacapone but not tolcapone, then multiply the total daily enteral levodopa dosage (mg) by 1.48
10. If enteral levodopa is taken with tolcapone, then multiply the total daily enteral levodopa dosage (mg) by 1.67
11. If immediate release or modified release pramipexole (e.g., Mirapex) is taken, multiply the daily dosage (mg/day of the dihydrochloride monohydrate salt) by 100
12. If immediate release or extended release ropinirole (e.g., Requip, Requip XL) is taken, multiply the dosage (mg/day) by 20
13. If a rotigotine patch (e.g., Neupro) is used, multiply the dosage (mg/day) by 30
14. If oral selegiline (e.g., Eldepryl) is taken, multiply the dosage (mg/day) by 10
15. If sublingual selegiline (e.g., Zelapar) is taken, multiply the dosage (mg/day) by 80
16. If oral rasagiline (e.g., Azilect) is taken, multiply the dosage (mg/day) by 100
17. If oral amantadine (e.g., Symmetrel) is taken, multiply the dosage (mg/day) by 1
18. If an injection or infusion of apomorphine (e.g., Apokyn) is taken, multiply the dosage (mg/day) by 10
19. Calculate total LEDD as the sum of quantities 7 through 18.

### 3.4. Determination of Sample Size

The primary efficacy measure is the change from baseline to the week 16 visit in the CDR COA. Based on a two-tailed test at alpha = 0.05 and assuming up to 15% loss to follow up, a total sample size of 80 randomized participants provides at least 80% power for a true treatment-dependent difference in 16-week change in CDR COA equal to an effect size of 0.69. Additional power will be obtained from analysis using a shared-baseline repeated-measures analysis of

variance. Effect sizes of similar magnitude were observed for several CDR measures in a 24-week trial of memantine in patients with PDD and dementia with Lewy bodies ([Wesnes et al. 2014](#)).

### **3.5. Analysis Samples**

The following analysis samples will be used for testing safety, tolerability, efficacy, and pharmacokinetic endpoints:

- Safety and Tolerability (ST) Sample: Participants who are eligible, randomized, and take at least one dose of study drug, classified according to the actual treatment received.
- Efficacy Modified Intent-to-treat (mITT) Sample: Participants who are eligible, randomized, have at least one valid pre-treatment and at least one valid post-treatment CDR COA measurement, and take at least one dose of study drug, classified according to their randomized treatment assignment. This sample will include observations made after discontinuation of study drug should any such participants remain on study.
- Efficacy Per-protocol (PP) Sample: Participants who are eligible, randomized, have at least one valid pre-treatment and one valid post-treatment CDR COA measurement, take at least one dose of study drug, and meet all other major protocol compliance criteria specified prior to unblinding, classified according to the actual treatment received. Observations made after permanent discontinuation of study drug (whether due to intolerance, early termination, loss to follow-up, or death) will be omitted, but completion of follow-up on study drug will not be required. Any other individual observations affected by important protocol deviations may also be excluded, as specified prior to unblinding.
- Pharmacokinetic (PK) Sample: Participants in the ST sample who have at least one valid determination of their plasma SYN120 concentration.

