Safety Evaluations	
Please refer to Table 1 for Schedule of Events/Evaluations.
 
Safety evaluations include:
 
• AE reports• UPDRS• Supine and standing pulse and blood pressure• 12-lead ECGs• Safety labs: hematology, chemistry, urinalysis• C-SSRS• Concomitant medication assessment
SYN120 Plasma Concentrations	
Blood samples will be collected for determination of SYN120 plasma concentrations [REDACTED] at Baseline (before the initiation of dosing), at Weeks 4, 8 and 16, and at Early Termination (if applicable). In addition, samples may be collected during unscheduled visits performed for AEs (optional, at the discretion of the Investigator).

Sample Size Justification	
The primary efficacy measure is the change from Baseline to Week 16 in the total score on the CDR Computerized Cognition Battery Continuity of Attention. Based on a two-tailed test at alpha = 0.05 and assuming up to 15% loss to follow up, a total sample size of 80 randomized participants provides at least 80% power for a true treatment-dependent difference in 16-week change in CDR Continuity of Attention equal to an effect size of 0.69. Additional power will be obtained from analysis using a shared-baseline repeated measures analysis of variance (ANOVA).

Analysis Populations	
Safety Analysis Set: The safety analysis set (SS) will consist of all randomized patients who received at least one dose of IMP.
 
Modified Intention-to-Treat Analysis Set: The modified intention-to-treat (mITT) analysis set will consist of all randomized patients who received at least one dose of IMP and who have at least one valid baseline and at least one valid post-baseline assessment of the primary efficacy endpoint.
 
Per-Protocol Analysis Set: The per-protocol (PP) analysis set will consist of a subset of the mITT analysis set, excluding any participants or observations potentially affected by important protocol deviations that might influence the validity of the data for testing efficacy and as specified in the Statistical Analysis Plan prior to breaking the blind.

PROTOCOL SYNOPSIS	

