10.1 Definition of Analysis Sets

Safety Sample (SS): The SS will consist of all randomized patients who received at least one dose of IMP.

Modified Intention-to-Treat (mITT) Sample: The mITT sample will consist of all randomized patients who received at least one dose of IMP and who have at least one valid baseline and at least one valid post-baseline assessment of the primary efficacy endpoint.

Per-Protocol Set (PP): The PP will consist of a subset of the mITT sample, excluding any participants or observations potentially affected by important protocol deviations that may influence the validity of the data for testing efficacy and as specified in the SAP prior to breaking the blind.

All safety variables will be summarized using the SS. All efficacy variables will be summarized using the mITT sample. The PP will be utilized for sensitivity analyses to estimate efficacy among participants tolerant of study drug and with less reliance on model assumptions required to extrapolate after any loss to follow up.

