## 1. INTRODUCTION

This Statistical Analysis Plan (SAP) defines the analysis samples, specifies the analysis, and guides the interpretation of results from the [SYN120-CL03](#) or SYNAPSE clinical trial. The SAP supplements the clinical protocol. Readers are encouraged to refer to the clinical protocol for details on the rationale for the intervention, eligibility criteria, conduct of the trial, clinical assessments and the timing of their use in the trial, definitions and reporting of adverse events, data management conventions, and regulatory oversight and compliance procedures. The reader is referred to the Investigator's Brochure for additional details on physiochemistry and pre-clinical and clinical pharmacokinetics and safety of the investigational product, SYN120.

In case of discrepancies between the SAP and the clinical protocol concerning matters of analysis, the SAP is authoritative. On all other matters, the clinical protocol is authoritative.

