### **2.5. Treatment Allocation**

At the baseline visit, eligible participants are randomly allocated in equal proportion to one of two treatment groups, SYN120 100 mg QD or placebo, according to a permuted-block randomization schedule with a block size of 4, stratified by site. The randomization schedule was prepared by computer program by the unblinded study statistician. Stratification by site is achieved by distributing to sites allotments of study drug kits that consist of a full block from the permuted-block schedule.

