- Maximum post-baseline suicidal behavior lethality and potential lethality

Reported proportions will use as their denominator all participants in the Safety and Tolerability sample (see [Section 3.5](#) below).

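### SAP 3.5 adds an undefined eligibility condition to the safety sample; read literally, it could drop dosed patients whom the protocol counts

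*SAP*

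**What the plan says.** The protocol defines the safety set twice, without any eligibility condition. Section 10.1 says "The SS will consist of all randomized patients who received at least one dose of IMP", and the synopsis (Analysis Populations) says "The safety analysis set (SS) will consist of all randomized patients who received at least one dose of IMP". Section 10.1 assigns all safety variables to that set, and section 10.5.1 analyses it as treated.

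SAP section 3.5 defines the Safety and Tolerability (ST) sample as "Participants who are eligible, randomized, and take at least one dose of study drug, classified according to the actual treatment received". The same extra word appears in the mITT and per-protocol (PP) definitions. The PK sample inherits it, being "Participants in the ST sample who have at least one valid determination of their plasma SYN120 concentration".

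On precedence, SAP section 1 states: "In case of discrepancies between the SAP and the clinical protocol concerning matters of analysis, the SAP is authoritative". The sentence after it leaves all other matters to the protocol.

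**The concern.** A safety set should contain every randomized patient exposed to study drug. Here *eligible* stands as a separate condition beside *randomized* and dosed, and neither document says how a dosed patient later found to breach an entry criterion is handled in the safety summaries. Because the SAP governs analysis, the broader protocol definition does not automatically repair the narrower one.

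What is at stake is the denominator, and possibly the numerator, of the reported safety results. SAP 3.2.2 says: "Reported proportions will use as their denominator all participants in the Safety and Tolerability sample". With about 40 patients per arm, the placement of a single patient visibly moves a percentage. If the word is left open, the decision on who counts could be taken after breaches, and the events in those patients, are known.

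**Working it through.** The plan states no figure on this point, so the check is a comparison of texts followed by an illustration on assumed counts.

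**1. Conditions for entering the safety sample**

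| Condition | Protocol synopsis and 10.1 | SAP 3.5 (ST) |
|---|---|---|
| Randomized | yes | yes |
| At least one dose taken | yes | yes |
| Eligible | not required | required |

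The only added restriction is eligibility.

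**2. What the word could mean**

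- *Reading (a): judged eligible before randomization.* SAP 2.5 supports this: "At the baseline visit, eligible participants are randomly allocated in equal proportion to one of two treatment groups". The word then adds nothing to *randomized*, and no one is removed.
- *Reading (b): a compliance filter.* The PP definition opens with the same word and, later in its list, requires participants to "meet all other major protocol compliance criteria specified prior to unblinding". The word *other* suggests that items already listed, eligibility among them, are compliance criteria too. SAP 2.3 also refers eligibility to the detailed protocol criteria, against which a programmer could check the data.

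**3. Where reading (b) would act**

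- Directly, because the ST sample is named: safety proportions (SAP 3.2.2), treatment-emergent adverse event tables (3.9.1), UPDRS safety models (3.9.6) and the PK sample (3.5).
- Possibly, through the opening line of 3.5, because no sample is named: the tolerability endpoint (3.2.3), laboratory, vital sign and blood pressure summaries (3.9.3 to 3.9.5), and compliance and time to discontinuation (3.10.2).
- Not affected: participant disposition (3.10.1).

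**4. How the question can arise**

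Under Protocol 7.16 the site decides QTcF eligibility on the machine reading, while the core laboratory gives the final interpretation, with the Baseline overread due within 24 hours. The first dose is given at the Baseline Visit (6.1 and 6.2.3.4). A patient can therefore be dosed before an overread above the exclusion 14 limit arrives. Section 7.16 supports still calling that patient eligible, but SAP 3.5 does not say which reading counts.

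The entry text also differs between places. Amantadine is listed as permitted in section 4.1 but not in the synopsis. Thyroid dose stability is counted back from Baseline in section 4.2 and from Screening in section 5.9.3. Those passages need reconciling in their own right, and they show that *eligible* does not define itself.

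**5. Size, by illustration**

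Inputs: 80 randomized, 40 per arm (Protocol 10.8). Assumptions: all 40 in an arm are dosed; k = 1 to 4 of them are later found ineligible; an adverse event is truly seen in 4 of the 40 (10.0%).

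- Share of the arm removed: 1/40 = 2.5% to 4/40 = 10%.
- Lowest reported proportion, if every removed patient had the event: (4 − k)/(40 − k).
- Highest reported proportion, if none did: 4/(40 − k).

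| k removed | Lowest | Highest |
|---|---|---|
| 1 | 3/39 = 7.7% | 4/39 = 10.3% |
| 2 | 2/38 = 5.3% | 4/38 = 10.5% |
| 3 | 1/37 = 2.7% | 4/37 = 10.8% |
| 4 | 0/36 = 0.0% | 4/36 = 11.1% |

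The chance that at least one of 80 dosed patients is affected, at an assumed breach rate p, is 1 − (1 − p)^80: 55% at p = 1%, 87% at 2.5% and 98% at 5%. Under reading (a) every change is zero.

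**The case against.** The strongest reply is that the documents favour the harmless reading. Protocol 3.1 settles final eligibility at the Baseline Visit. Sections 6.2.3.1 and 6.2.3.4 place randomization after eligibility is confirmed and restrict it to patients who meet the entry criteria. SAP 2.4 follows the same order, so the ST wording may simply retrace participant flow. When a patient becomes eligible is arguably a matter of conduct, on which the protocol governs. No procedure exists for re-judging eligibility after dosing, and deviation-based exclusions are attached only to the PP sample. The PP wording is a weak cue, since *other* follows a whole list. The 0/36 figure is a constructed extreme.

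Much of this stands. Reading (a) is well supported, no intent to exclude anyone is shown, the PP cue is not conclusive, and the effect on summaries that name no sample is an inference.

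It does not close the gap. Beside *randomized*, the word does no work unless it filters; SAP 2.3 ties it to criteria that can be checked; and no text keeps a dosed patient later found in breach in the safety tables. A statement that *eligible* means judged eligible at randomization would resolve the ambiguity, but the SAP has no such statement.

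**Conclusion.** The concern holds. SAP 3.5 states an inclusion rule for the safety sample that is narrower than the protocol's and, applied literally, omits exposed patients whom the protocol includes. It is an ambiguity with a possible safety consequence, not a demonstrated loss of patients.

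The size is zero under reading (a). Under reading (b) it depends on the number of breaches, their arm and their event experience, none of which the documents give, so no direction of between-arm effect can be claimed. The 1 to 4 patients and the 4/40 event count are assumptions. Event collection and safety monitoring do not depend on this definition; the issue is confined to who is counted in the reported summaries. It should be fixed, with medium confidence that it would matter in practice.

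**What to change.** Delete *eligible* from the ST definition in SAP 3.5 and leave the rest of the sentence as it is, including classification by treatment actually received. The ST sample then matches the safety set in Protocol 10.1, and the PK sample follows. If the word is kept, say that it means judged eligible at randomization and that no dosed patient is removed from safety summaries because of a later finding.

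For consistency with Protocol 10.1, also delete it from the mITT definition and deal with entry-criterion breaches in the PP sample. This second change is alignment with the protocol, not the correction of a demonstrated bias.

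The cost is a one-word deletion in each of two definitions, made before unblinding. It needs no extra data and changes neither the sample size nor the models.
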